CTCAE	Common Terminology Criteria for Adverse Events
DLT	Dose limiting toxicity
DM4	N2'-[4-[(3-carboxypropyl)dithio]-4-methyl-1-oxo-2-sulfopentyl]-N2'-deacetylmaytansine
DNA	Deoxyribonucleic acid
DoR	Duration of Response
EC	Endometrial cancer

Abbreviation or Specialist Term	Explanation
ECOG	Eastern Cooperative Oncology Group
eCRF	Electronic case report form
ECG	Electrocardiogram
ELISA	Enzyme-linked immunosorbent assay
EOC	Epithelial Ovarian Cancer
FDA	Food and Drug Administration
FFPE	Formalin-fixed, paraffin embedded
FIH	First in Human
FOLR1, FRα	Folate receptor 1/Folate receptor α
GCIG	Gynecologic cancer intergroup
GCP	Good Clinical Practice
GLP	Good Laboratory Practice
GPI	Glycophosphatedylinositol
HADA	Human anti-drug antibody
НАНА	Human anti-human antibody
Hct	Hematocrit
HED	Human Equivalent Dose
Hgb	Hemoglobin
HIV	Human Immunodeficiency Virus
HNSTD	Highest non-severely toxic dose
IBW	Ideal body weight
ICF	Informed consent form
ICH	International Conference on Harmonization
IEC	Independent Ethics Committee
IHC	Immunohistochemistry
IMGN	ImmunoGen
IND	Investigational New Drug
INR	International Normalized Ratio
IRB	Institutional Review Board
IV	Intravenous
LBW	Lean body weight
LDH	Lactic acid dehydrogenase
LFT	Liver function test

Abbreviation or Specialist Term	Explanation
Mab	Monoclonal antibody
MedDRA	Medical Dictionary for Regulatory Activities
MRI	Magnetic Resonance Imaging
MRSD	Maximum Recommended Starting Dose
MTD	Maximum tolerated dose
NCI	National Cancer Institute
NSCLC	Non-small cell lung cancer
ORR	Objective response rate
OS	Overall survival
PBMC	Peripheral blood mononuclear cell
PCFT	Proton-coupled folate transporter
PD	Progressive disease
Pd	Pharmacodynamic(s)
PET	Positron emission testing
PFS	Progression-free survival
PGP	p-glycoprotein
PK	Pharmacokinetics
PO	Per orem (by mouth)
PR	Partial response/remission
PT	Prothrombin time
qPCR	Quantitative real time polymerase chain reaction
RBC	Red blood cell (count)
RNA	Ribonucleic acid
RP2D	Recommended phase 2 dose
SAE	Serious adverse event
SAP	Statistical Analysis Plan
SD	Stable disease
STD	Standard Deviation
SGOT	Serum glutamic oxaloacetic transaminase (AST)
SGPT	Serum glutamic pyruvic transaminase (ALT)
SOC	Standard of Care
SOP	Standard Operating Procedure
SoD	Sum of the longest diameters

Abbreviation or Specialist Term	Explanation
STD	Severely Toxic Dose
SUSAR	Suspected Unexpected Serious Adverse Reaction
t _{1/2}	Half-life
TBW	Total body weight
TTP	Time to progression
ULN	Upper limit of normal
US	United States
VHL	Von Hippel Lindau
Vss	Volume of distribution at steady state
WBC	White blood cell (count)
WCBP	Woman of child bearing potential
WHO	World Health Organization
WHO-DD	World Health Organization –Drug Dictionary

PROTOCOL SYNOPSIS

Title of Study: A Phase 1, First-in-Human Study to Evaluate the Safety, Tolerability, Pharmacokinetics and Pharmacodynamics of IMGN853 in Adults with Ovarian Cancer and other FOLR1-positive Solid Tumors

Study center(s): up to 10 in the United States and 1 site in Canada

Studied period (months): Approximately 50 months

(including follow up)

First patient enrolled: June 28, 2012 First patient dosed: July 9, 2012 Phase of development: 1

Purpose/rationale: IMGN853 is a specific, targeted antibody maytansinoid conjugate (AMC) that binds with high affinity to folate receptor 1 (FOLR1), a GPI-linked protein, which is highly expressed on the surface of solid tumors, particularly epithelial ovarian cancer, endometrial cancer, NSCLC and renal cell cancer. IMGN853 consists of a humanized anti-FOLR1 monoclonal antibody (M9346A) attached via a disulfide containing linker to the cytotoxic maytansinoid, DM4. Once released within the target cell, DM4 acts as an anti-mitotic agent that inhibits tubulin polymerization and microtubule assembly, resulting in cell cycle arrest and apoptosis.

In vitro, IMGN853 binds cell surface FOLR1 with high apparent affinity (\leq 0.1 nM) and shows potent (IC₅₀ \leq 1 nM) and selective cytotoxicity against tumor cells expressing FOLR1. IMGN853 additionally demonstrates significant activity against FOLR1-positive xenografts, with partial and complete remissions observed in ovarian and NSCLC models. Together with the selective upregulation of FOLR1 in solid tumors, these results provide the rationale for exploring the clinical utility of IMGN853.

This first-in-human (FIH) Phase 1 study is designed to establish the maximum tolerated dose (MTD) and determine the recommended Phase 2 dose (RP2D) of IMGN853 when administered intravenously as a single agent in adult patients with relapsed or refractory ovarian cancer and other FOLR1-positive solid tumors. The safety, tolerability, pharmacokinetics (PK), pharmacodynamics (Pd), immunogenicity, and preliminary anti-tumor activity of IMGN853 will be characterized. Two dosing schedules will be evaluated in this study:

Schedule A: IMGN853 administered on Day 1, with cycles repeating every 21 days (Q3W)

Schedule B: IMGN853 administered on Days 1, 8, and 15, with cycles repeating every 28 days (modified weekly)

Amendment 10 Update: further evaluation of dosing Schedule B has been discontinued in this study.

Objectives: The primary objectives of this study are to determine the MTD (dose escalation) and define the RP2D (MTD expansion) for the two dosing schedules. The secondary objectives are to evaluate the safety and tolerability of IMGN853 and to characterize the PK, Pd, immunogenicity and preliminary efficacy of IMGN853. The exploratory objectives are to determine any association between FOLR1 expression levels and clinical response and to evaluate potential biomarkers in blood and tumor tissue that might predict response to IMGN853.

The study objectives are detailed in Sections 2.1, 2.3, and 2.5, and corresponding study endpoints are defined in Sections 2.2, 2.4, and 2.6.

Number of patients (planned):

ImmunoGen, Inc. Confidential Page 8 of 138

It is estimated that 209 patients* will be enrolled into the study.

- Dose Escalation Phase: (1) Schedule A: 44 patients (2) Schedule B: 25 patients
- Dose Expansion Cohort 1: Patients with epithelial ovarian cancer (EOC) which is resistant to platinum-based therapy: 40 patients
- Dose Expansion Cohort 2: Advanced or recurrent uterine cancer: 20 patients
- Dose Expansion Cohort 3: Patients with relapsed EOC, which is amenable to biopsy: 20 patients
- Dose Expansion Cohort 4: Relapsed/refractory NSCLC adenocarcinoma or bronchioloalveolar carcinoma (BAC): 20 patients
- Dose Expansion Cohort 5: Patients with EOC which has relapsed following platinum-based therapy: 40 patients; this cohort of patients will receive prophylactic corticosteroid eye drops

*NOTE: Every effort will be made to ensure the requisite number of patients are accrued in each cohort, and to this end, communications with the site will be monitored carefully. There are instances however, where, as a result of simultaneous screening activities, patients may qualify for the study at the same time, resulting in slight over-enrollment in individual cohorts

[figure not shown]
The estimated study duration is approximately 50 months for patient accrual, dosing, and follow up.

Study Design Overview and Schema: This is an open label, Phase 1, non-randomized, FIH study of IMGN853 in adult patients with FOLR1-positive solid tumors that have relapsed, or are refractory to standard therapies. Two dosing schedules will be evaluated in this study:

Schedule A: IMGN853 administered on Day 1, with cycles repeating every 21 days (Q3W) The dose escalation phase will initially enroll 1 patient each at the first four dose levels. Patients will be enrolled to subsequent cohorts using a standard 3+3 design, with each cohort consisting of 3 or 4 to 6 patients. **Amendment 10 Update:** Dose escalation is complete and the MTD was determined to be 6 mg/kg (AIBW) and available data available to date indicate that the MTD is equal to the RP2D. Schedule A is currently being evaluated in the dose expansion cohorts.

Schedule B: IMGN853 administered on Days 1, 8, and 15, with cycles repeating every 28 days (modified weekly)

ImmunoGen, Inc. Confidential Page 9 of 138

The starting dose of IMGN853 was 1.1 mg/kg, which was 1/3 the 3.3 mg/kg dose level, which was deemed clinically safe in nine patients on a Q3W schedule. All doses were calculated according to adjusted ideal body weight (AIBW). Patients were enrolled in cohorts of 3 to 6 patients and the MTD was determined to be 2.0 mg/kg (AIBW). The CRC convened to review safety, PK and efficacy data from the dose escalation cohorts, as well as available data from patients treated on Schedule A. These findings were presented at the ASCO annual meeting (Borghei 2015).

The modified weekly schedule did not provide any apparent safety or efficacy advantage. Based on safety and overall response data collected through May 2015, the CRC determined that all new patients will receive IMGN853 treatment according to Schedule A (Q3W) only (Figure 2). All new patients enrolled in the trial will receive IMGN853 at the MTD of 6 mg/kg once every three weeks. Of note, safety data that are available to date indicate that the MTD is equal to the RP2D.

The study design and methodology is outlined in detail in Section 4.1.

Main Criteria for Study Eligibility:

Diagnosis, allowable prior therapy and disease measurability:

• Dose Escalation Phase:

All patients must have a pathologically documented, definitively diagnosed, advanced solid tumor that is refractory to standard treatment, for which no standard treatment is available, or the patient refuses standard therapy. Patients may have measurable or non-measurable disease. There is no upper limit on the number of prior treatment regimens the patient may have received, and prior treatment with folate receptor-targeting investigational agents is allowed.

Enrollment (without prior documented FOLR1 expression) will be limited to the following histologic subtypes, which have a high incidence of FOLR1 positivity:

- Serous or endometrioid EOC, primary peritoneal cancer, or fallopian tube cancer
- Serous or endometrioid endometrial cancer
- Adenocarcinoma or Bronchioloalveolar carcinoma (BAC) Non-small cell lung cancer (NSCLC)

Patients with tumor types not listed above must have confirmation of $\geq 1\%$ tumor cells with ≥ 1 FOLR1 positivity by immunohistochemical staining (IHC) prior to enrollment (see the Laboratory Manual for IHC screening procedures). The tumor samples will be analyzed for folate receptor alpha FR α expression in the Companion Diagnostics Pharma Services CAP-accredited and CLIA-certified laboratory and Pathology Services at Ventana Medical Systems, Inc.

• Dose Expansion Phase:

- Dose Expansion Cohort 1 patients with platinum resistant EOC
 - Patients must have histologically-confirmed EOC, primary peritoneal cancer or fallopian tube cancer that is resistant to platinum therapy.
 - Patients must have platinum-resistant ovarian cancer, which is defined as disease that responded to primary platinum therapy and then progressed within six months or disease that progressed during or within six months of completing subsequent platinum therapy.
 - Patients must meet the minimum requirement of FOLR1 positivity by IHC (≥25% of tumor staining at ≥2+ intensity).
 - Patients with primary platinum refractory disease (those who have not responded to a platinum-based regimen or experienced disease recurrence within three months of completing their first platinum-based regimen) are excluded.
 - o Patients with clear cell or low grade ovarian cancer are excluded.
 - o Patients should not have received more than five prior systemic treatment regimens.
 - Patients must have at least one lesion that meets the definition of measurable according to RECIST 1.1 (Appendix E).
- Dose Expansion Cohort 2

 patients with advanced or recurrent uterine malignancies

ImmunoGen, Inc. Confidential Page 11 of 138

- Patients must have histologically-confirmed diagnosis of advanced or recurrent uterine cancer
- Patients must have confirmation of FOLR1 expression by IHC (enrollment cut-off H score ≥100).
- Patients must have received at least one platinum-based chemotherapy regimen and no more than five prior systemic treatment regimens (including cytotoxic chemotherapy, hormonal therapy, and targeted therapy, or any other investigational treatment in the adjuvant or the metastatic setting) for EC.
- The subject must have at least one lesion that is measurable on CT or MRI scan determined by investigator per RECIST Version 1.1

• Dose Expansion Cohort 3, relapsed ovarian cancer, which is amenable to biopsy:

- Patients must have relapsed EOC, primary peritoneal cancer or fallopian tube cancer; patients with primary refractory disease (those who have not responded to a platinum-based regimen or experienced disease recurrence within three months of completing their first platinum-based regimen) are excluded.
- o Patients with clear cell or low grade ovarian cancer are excluded.
- Patients must be willing to undergo tumor biopsy prior to the first dose of IMGN853 and on Cycle 2, Day 8±3 days.
- Patients must meet the minimum requirement of FOLR1 positivity by IHC (≥25% of tumor staining at ≥2+ intensity).
- There is no upper limit on the number of prior treatment regimens (cytotoxic and/or targeted therapies) the patient may have received.
- Patients may have measurable or non-measurable disease (such as large abdominal masses that cannot be accurately measured) as defined by RECIST 1.1 (Appendix E).

• Dose Expansion Cohort 4, relapsed/refractory NSCLC adenocarcinoma or BAC

- Patients must have histologically or cytologically-confirmed NSCLC adenocarcinoma or BAC, and must be refractory to or cannot tolerate standard of care (SOC).
- Patients must meet the minimum requirement of FOLR1 positivity by IHC (≥25% of tumor staining at ≥1+ intensity).
- There is no upper limit on the number of prior treatment regimens (cytotoxic and/or targeted therapies) the patient may have received.
- o Patients may have measurable or non-measurable disease (such as large masses that cannot be accurately measured) as defined by RECIST 1.1 (Appendix E).
- **Dose Expansion Cohort 5** Patients enrolled in this cohort will receive corticosteroid eye drops as primary prophylaxis to assess whether they reduce the risk or severity of blurred vision and/or keratopathy observed following treatment with IMGN853.

ImmunoGen, Inc. Confidential Page 12 of 138

- Patients must have one of the following pathologically documented, definitively diagnosed tumor types:
 - Advanced EOC
 - Primary peritoneal cancer
 - Fallopian tube cancer
- o Patients must have received at least 3 but not more than 4 prior systemic treatment regimens
- Patients must have confirmation of \geq 2 FOLR1 positivity by IHC (\geq 25% of tumor staining at \geq 2+ intensity).
- Patients with primary platinum refractory disease (those who have not responded to a platinum-based regimen or experienced disease recurrence within three months of completing their first platinum-based regimen) are excluded.
- o Patients with clear cell or low grade ovarian cancer are excluded.
- Patients must be willing and able to self-administer corticosteroid eye drops four times a day, for the first 10 days of each cycle, during active study treatment.
- Patients must have measurable or non-measurable disease (such as large abdominal masses that cannot be accurately measured) per RECIST 1.1 (Appendix E).

Main Eligibility Criteria for All Patients:

- Patients with CNS metastases are eligible if they meet the requirements outlined in the Inclusion Criteria (Section 3.1.1). Other standard inclusion criteria will be employed and are detailed in Section 3.1.1.
- Patients will be excluded if they have > Grade 1 peripheral neuropathy, or an active or chronic corneal disorder.
- Patients who have received prior allogeneic or autologous bone marrow transplants will not be enrolled.

Additional exclusion criteria are detailed in Section 3.1.2.

Investigational product, dosage, and mode of administration: Two IMGN853 administration schedules will be investigated:

Schedule A: IMGN853 administered IV on Day 1, with cycles repeating every 21 days (Q3W)

- The starting dose was 0.15 mg/kg based on total body weight.
- With amendment 5, the starting dose using adjusted ideal body weight (AIBW) was 5.0 mg/kg.

Schedule B: IMGN853 administered IV on Days 1, 8, and 15, with cycles repeating every 28 days (modified weekly schedule)

- The starting dose was 1.1 mg/kg, calculated using AIBW.
- The MTD was 2.0 mg/kg (AIBW). This schedule of administration will not be further evaluated in this study.

The dose of IMGN853, used in both Schedule A and Schedule B dose escalation schedules and in all expansion cohorts, will be calculated using adjusted ideal body weight (AIBW). Treatment guidelines and dose modification guidelines are detailed in Section 5.9.

ImmunoGen, Inc. Confidential Page 13 of 138

Duration of treatment: The period of observation extends from the time the patient receives the first dose of IMGN853 until the final follow-up study visit. Patients will continue to receive IMGN853 until they develop progressive disease (PD), unacceptable toxicity, withdraw consent, or until the Sponsor terminates the study. Patients who discontinue study drug for reasons other than PD will be followed until PD or start of new anti-cancer therapy, or death, whichever occurs first.

Statistical methods: There will be no formal hypothesis testing. All descriptive statistical analyses will be performed using the most recently released and available SAS statistical software, unless otherwise noted. For categorical variables, the number and percent of each category within a parameter will be calculated. For continuous variables, the sample size (n), mean, median, and standard deviation, as well as the minimum and maximum values, will be presented. Missing data will not be imputed unless otherwise stated. There will be a detailed description of patient disposition; patient demographics and baseline characteristics will be summarized. PK data will be presented descriptively and graphically.

No formal interim analysis is planned for this study. However, a review of safety data and available preliminary PK data will be conducted by the Cohort Review Committee (CRC, Section 4.1.2) upon completion of each dose escalation cohort, and every 2 or 4 weeks during MTD Dose Expansion. A statistical analysis plan (SAP) will fully describe the planned analyses for this study.

Sample Size: Ascending doses of IMGN853 will be evaluated to identify the MTD for both dosing schedules. The actual number of patients accrued during this phase will be determined largely by the findings observed during the course of their treatment.

Following identification of the MTD for Schedule A (Q3W), there will be an expansion phase which will accrue two cohorts each at the MTD:

(1) Dose Expansion Cohort 1: 40 patients with platinum resistant EOC. The sample size of Schedule A Cohort 1 was increased from 20 to 40 to better define the frequency of ocular adverse events and assess the impact of the proposed toxicity management guidelines.

Given a sample size of 40 patients, the power to detect a difference of 20% (rate of Blurry vision drop from 50% to 30%) is 68% using one-sided alpha of 20% and Chi-Square test statistics.(2) Dose Expansion Cohort 2: 20 patients with advanced or recurrent uterine cancer.

Amendment 10 Update: The CRC committee met and reviewed the available safety and response data. The decision was made to proceed with Schedule A only. All new patients enrolled in the trial will receive IMGN853 at the MTD of 6 mg/kg once every three weeks. Safety data available to date indicate that the MTD is equal to the RP2D.

- (3) Dose Expansion Cohort 3: 20 patients with relapsed ovarian cancer, which is amenable to biopsy.
- (4) Dose Expansion Cohort 4: 20 patients with relapsed/refractory NSCLC adenocarcinoma or BAC.
- (5) Dose Expansion Cohort 5: 40 patients with relapsed EOC. In this cohort of patients, the use of corticosteroid eye drops as part of the management plan for treatment-emergent ocular adverse events will be evaluated. Given a sample size of 40 patients, the power to detect a difference of 20% (rate of Blurry vision decrease from 50% to 30%) is 68% using one-sided alpha of 20% and Chi-Square test statistics.

ImmunoGen, Inc. Confidential Page 14 of 138

Cohorts evaluated under two dosing schedules, will be referenced in clinical study documents by both cohort number and schedule (e.g. Cohort 1A).

If the true DLT rate at the MTD is 10-20%, there is a 98.5-99.9% probability of observing at least 1 dose limiting toxicity (DLT) in the 40 patient cohorts. If the true response rate at the MTD is 20%, there is a 99.9% probability of observing at least 1 response in the 40 patient cohorts.

Approximately 209 patients will be enrolled allowing for dropouts and expansion of dose escalation cohorts as needed.

TABLE OF CONTENTS

SPONSO	R SIGNATURE PAGE	2
LIST OF	ABBREVIATIONS	4
PROTOC	COL SYNOPSIS	8
TABLE (OF CONTENTS	16
1.	INTRODUCTION	25
1.1.	Target Background	25
1.2.	IMGN853	28
1.3.	Epithelial Ovarian Cancer (EOC), Endometrial Cancer (EC) and NSCLC	29
1.3.1.	EOC	29
1.3.2.	NSCLC	30
1.3.3.	Endometrial Carcinoma	30
1.4.	Non-Clinical Studies of IMGN 853	30
1.4.1.	Pharmacology	30
1.4.2.	Pharmacokinetics	31
1.4.2.1.	Single Dose Non-GLP Studies in CD-1 Mice	31
1.4.2.2.	Single Dose Toxicokinetics of IMGN853 in Cynomolgus Monkeys	31
1.4.2.3.	PK of Free DM4 in Cynomolgus Monkeys	32
1.4.3.	Toxicology	32
1.4.3.1.	Single-Dose GLP Cynomolgus Monkey Toxicology Study	32

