3. STUDY POPULATION

3.1. Criteria for Selection of Patient Population

- 1. Diagnosis, allowable prior therapy, and disease measurability requirements:
- A. **Dose Escalation Phase:** All patients must have a pathologically documented, definitively diagnosed, advanced solid tumor that is refractory to standard treatment, for which no standard treatment is available, or the patient refuses standard therapy. Enrollment without prior documentation of tumor FOLR1 expression will be limited to the following histologic subtypes, which have a high incidence of FOLR1 positivity:
 - a. Serous or endometrioid epithelial ovarian cancer, primary peritoneal cancer, or fallopian tube cancer
 - b. Serous or endometrioid endometrial cancer
 - c. Adenocarcinoma or BAC NSCLC
 - d. Additional tumor types may be eligible, but require documented expression of FOLR1
 (≥1% of tumor staining at ≥1+ intensity) by IHC (see Laboratory Manual for IHC screening procedures)
 - e. There is no upper limit on the number of prior cytotoxic or targeted therapies the patient may have received. Patients may have received prior treatment with investigational compounds targeting folate receptor.
 - f. Patients must have measurable or non-measurable disease (such as large abdominal masses that cannot be accurately measured) according to RECIST 1.1 (Appendix E).
- B. **Dose Expansion Cohort 1:** Patients must have EOC, which is resistant to platinum-based chemotherapy:
 - a. Patients must have received prior platinum-based therapy for management of disease.
 - b. Patients must have histologically-confirmed EOC, primary peritoneal cancer or fallopian tube cancer.
 - c. Patients must have platinum-resistant ovarian cancer, which is defined as disease that responded to primary platinum therapy and then progressed within six months or disease that progressed during or within six months of completing subsequent platinum therapy.
 - d. Patients must meet the minimum requirement of FOLR1 positivity by IHC (≥25% of tumor staining at ≥2+ intensity).
 - e. Patients with primary platinum refractory disease (those who have not responded to a platinum-based regimen or experienced disease recurrence within three months of completing their first platinum-based regimen) are excluded.
 - f. Patients with clear cell or low grade ovarian cancer are excluded.
 - g. Patients must not have received more than five prior systemic treatment regimens.

ImmunoGen, Inc. Confidential Page 50 of 138

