5.8.2. Premedication with Corticosteroid Eye Drops (Dose Expansion Cohort#5 ONLY)

All patients enrolled into Cohort Expansion 5 will be instructed to self-administer 1% prednisolone (Pred Forte[®] or generic equivalent) six times daily on Days 1-5 and four times daily on Days 6-10 of each cycle during the study (Figure 4).

[figure not shown]
These medications will be prescribed by the treating physician and will be sourced by the site. Patients will record their eye drop administration in a patient diary, which will be entered on the CRF.

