11.1. Sample Size

Ascending doses of IMGN853 are to be evaluated to identify the MTD for both dosing schedules. The actual number of patients accrued during this phase will be determined largely by the findings observed during the course of their treatment.

Following identification of the MTD for Schedule A (Q3W), there was an expansion phase which initially accrued two cohorts at the MTD: (1) Dose Expansion Cohort 1-40 patients with platinum resistant EOC. (2) Dose Expansion Cohort #2-20 patients with advanced or recurrent uterine cancer. Once the Schedule B MTD (modified weekly) was established, the CRC convened to review safety, PK and efficacy results from the both schedules as well as preliminary data from the Expansion Cohorts 1 and 2, with the Q3W schedule of administration. The CRC recommended use of Schedule A for all future cohorts. Three additional MTD Expansion Cohorts will enroll the following patients: (3) Dose Expansion Cohort 3-20 patients with relapsed ovarian cancer, which is amenable to biopsy (4) Dose Expansion Cohort 4-20 patients with relapsed/refractory NSCLC adenocarcinoma, and (5) 40 patients with platinum resistant EOC who will receive daily treatment with corticosteroid-containing eye drops.

If the true DLT rate at the MTD is 10-20%, there is an 98.5-99.9% probability of observing at least one DLT in each 40 patient cohort. If the true response rate at the MTD is 20%, there is a 99.9% probability of observing at least one response in each 40 patient cohort.

ImmunoGen, Inc. Confidential Page 106 of 138

x (Number	True Event Rate			
Observed)	10%	20%	30%	
1	0.985	0.999	0.999	
2	0.919	0.998	0.999	
3	0.777	0.992	0.999	
4	0.577	0.972	0.999	
5	0.371	0.924	0.997	
6	0.206	0.838	0.991	

Table 16: Probability of Observing $\geq x$ Events (Response or DLT) For a 40 patient Cohort

Given a sample size of 40 patients, the power to detect a difference of 20% (rate of Blurry vision decrease from 50% to 30%) is 68% using one-sided alpha of 20% and Chi-Square test statistics.

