2.3.4. Treatment Randomization

No randomization will be performed in this study.

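### The 68% power for blurred vision fits a 20 vs 20 comparison, but Cohort 5 is one group of 40 who all receive steroid drops, and no comparator is named

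*Protocol*

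**What the plan says.** The sample-size text of the protocol synopsis makes the power claim twice.

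- **Cohort 1:** "Given a sample size of 40 patients, the power to detect a difference of 20% (rate of Blurry vision drop from 50% to 30" per cent is put at 68%. This directly follows the explanation that the cohort grew from 20 to 40 patients, to define ocular event frequency better and to assess the toxicity management guidelines.
- **Cohort 5:** in this cohort "the use of corticosteroid eye drops as part of the management plan for treatment-emergent ocular adverse events will be evaluated". The synopsis then claims, for its 40 members, that "the power to detect a difference of 20% (rate of Blurry vision decrease from 50% to 30%) is 68% using one-sided alpha of 20" per cent, by chi-square.

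Section 11.1 makes the claim a third time ("Given a sample size of 40 patients, the power to detect a difference of 20% (rate of Blurry vision decrease from 50% to 30" per cent), after Table 16 and without naming a cohort.

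On design, Section 5.8.2 says: "All patients enrolled into Cohort Expansion 5 will be instructed to self-administer 1% prednisolone". SAP 2.3.4 says: "No randomization will be performed in this study". On inference, the synopsis says: "There will be no formal hypothesis testing", and Section 1.6 agrees.

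Evaluating the prophylactic drops is a secondary objective (Protocol 2.3, SAP 2.1.2). SAP 2.3.3.2 carries over the DLT and response probabilities but not the power sentence. SAP 6.2 plans tables of incidence, grade, time to onset and action taken for ocular events, and SAP 3.8 displays summary tables by dose cohort or treatment group.

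**The concern.** A power figure describes a comparison, so the reader needs to know both sides of it. For Cohort 5 the documents give one side only: 40 treated patients. They name no control cohort, no historical rate and no split within the cohort, and they give no source for the 50%.

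At stake is the interpretation of a stated secondary objective. Whether the drops prevent or lessen ocular toxicity cannot be judged without saying compared with what, and the SAP text does not supply the missing side. It specifies no difference between Cohort 5 and any comparator. Its subgroup list for adverse events pools Cohorts 1, 3 and 5 and divides them by platinum status, prior regimens and receptor staining, never by use of steroid drops.

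**Working it through.** **Inputs** (synopsis, Sample Size; Section 11.1): rates 50% and 30%, one-sided alpha 20% (z = 0.8416), chi-square, 40 patients, stated power 68%. The text does not say whether 40 is a total or a group size.

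**Two-group formula.** Power = Φ{[(p1 − p2) − z·s0] / s1}, where s0 = √[p̄(1 − p̄)(1/n1 + 1/n2)] and s1 = √[p1(1 − p1)/n1 + p2(1 − p2)/n2].

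**Step 1: reproduce the stated figure, 20 vs 20.**
- p̄ = 0.40; s0 = √(0.24 × 0.10) = 0.1549; s1 = √(0.0125 + 0.0105) = 0.1517.
- (0.20 − 0.8416 × 0.1549) / 0.1517 = 0.459, so power = 67.7%. This matches 68%. With continuity correction it would be 55.2%.

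**Step 2: two groups of 40.**
- s0 = 0.1095; s1 = 0.1072; (0.20 − 0.8416 × 0.1095) / 0.1072 = 1.005, so power = 84.3% (78.0% with continuity correction).

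**Step 3: 40 patients against a fixed 50%.**
- Exact binomial: P(X ≤ 16 | 40, 0.50) = 13.4%, while P(X ≤ 17) = 21.5% exceeds the 20% limit. The rule is therefore to reject at 16 or fewer.
- Power = P(X ≤ 16 | 40, 0.30) = 93.7%. The normal approximation gives 96.7%.

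**Step 4: other allocations.** Some uneven splits also come close: 13 comparator patients vs 40 gives 67.7%, and 16 vs 24 gives 66.9%. The documents describe neither.

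**Step 5: Cohort 1 as comparator, 40 vs 40, Cohort 5 at 30%.** The Cohort 1 sentence plans for that cohort to fall from 50% to 30%, so its rate cannot simply be held at 50%.

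| Cohort 1 rate | Power | Source of the rate |
|---|---|---|
| 50% | 84% | protocol |
| 45% | 71% | assumed |
| 40% | 54% | assumed |
| 35% | 36% | assumed |
| 30% | 20% (alpha only) | protocol |

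**Step 6: precision.** If 12/40 in Cohort 5 and 20/40 in a comparator had blurred vision, the difference would be −20 points, with a Newcombe 95% CI of −39.0 to +1.4 points. Two percentages shown side by side would hide that width.

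**The case against.** The strongest reply is that nothing turns on the figure. No formal testing is planned, the SAP does not carry the sentence, and 68% is correct for 20 vs 20. All of that stands and limits the consequence. It does not make the published figure describe the cohort to which it is attached.

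It can also be said that drops define Cohort 5, so display by cohort already separates the patients who use them, and that the table shells are in a separate document (SAP 1.1). This too stands in part: one cannot say that no interval will ever be shown, only that the SAP text specifies none.

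A reader might infer three stronger things that the documents do not support.

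- **Cohort 5 is too small.** Against a fixed 50%, power is above 68%. Against Cohort 1 it may be above or below, depending on a rate not known in advance.
- **The sentence was carried over from a comparison of the first 20 with the next 20 patients in Cohort 1.** The growth of that cohort from 20 to 40 makes this possible, but no passage says so. Cohort 1 names no comparator either.
- **The correct figure is 84%.** That holds only if Cohort 1 stays at 50%, which sits badly beside the protocol's own plan for Cohort 1.

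**Conclusion.** The point holds as a mismatch between a stated power and a design, not as a calculation error. The 68% matches 20 vs 20 without continuity correction. Cohort 5 is a single non-randomised group of 40, all on drops, with no comparator named, so it does not have that power. The figures that could apply are about 94% against a fixed 50%, or anywhere from 84% to 20% against 40 Cohort 1 patients as the Cohort 1 rate goes from 50% to 30%.

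These results assume a true Cohort 5 rate of 30%, one-sided alpha of 20%, all 40 patients evaluable, and no allowance for differences between cohorts. No decision rule fails. The defect is that the reader cannot tell what the drops are to be compared with. It is worth correcting because it concerns a secondary objective and the repair is cheap.

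**What to change.** **Protocol: synopsis Cohort 1, synopsis Cohort 5 and Section 11.1.** Choose one course and apply it in all three places.

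- Delete the power sentence, as inconsistent with the statement that no hypothesis will be formally tested; or
- Name the comparator and restate the power for it. For Cohort 5 against a fixed 50%: about 94%, with the rule (16 or fewer of 40) and the true alpha (13.4%). Against Cohort 1: give the whole range in the table above, with the in-between rates labelled as assumptions; 84% should not stand alone. Keep 68% only if it is labelled as 20 vs 20 and the two groups are identified.

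**SAP 6.2.** Add the difference in blurred-vision and keratopathy incidence between Cohort 5 and the named comparator without prophylaxis (Cohort 1, for example), with a 95% CI, the level SAP 5.1.2 already uses for response rate. Label it descriptive and non-randomised. Note the different eligibility limits in Protocol 3.1: for Cohort 1, "Patients must not have received more than five prior systemic treatment regimens"; for Cohort 5, three or four.

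**Cost.** Wording in three protocol places and one extra table from data already collected, with no added patients or visits. The comparison will be confounded and must be read as such.

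Separately, Figure 3 and Section 11.1 call Cohort 5 platinum resistant, while the synopsis patient numbers and Sections 1.7, 3.1, 4.1.1 and 4.1.5 do not require it. Those passages must be reconciled before platinum status is listed as a difference between the cohorts.
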